7.4 Patient Death

7.4.1. Procedure for recording and reporting Patient Death

7.4.2. All patient deaths are to be documented and reported to the sponsor maximum 3 calendar days after becoming aware of the event. Should death occur, the investigator is requested to record death information in the hospital records and immediately document the information on the Death Form. By completing the form the sponsor will be notified. Refer to

and Appendix C: Data Collection Method. In case of EDC failure, notify Sponsor via Fax or via [contact].

All efforts (including use of national death registries) should be made to identify, precisely characterize, and appropriately classify any death.

Patient death is an outcome of a serious adverse event (SAE). All efforts to get SAE details should be made and the Adverse Event eCRF must be completed.

If available, the explanted Portico valve should be returned to SJM per instructions provided in Appendix K: Explant, Return, and Analysis of Valve and Appendix L: Instructions for device return - Large and Small Kits.

The patient's death is an early conclusion of the patient's participation in the investigation. Therefore, the investigator is requested to complete the termination form. The investigator must notify the EC/IRB, if appropriate, in accordance with national and local laws and regulations.

7.5 Criteria and procedures for patient withdrawal or discontinuation

Each patient should remain in the investigation until completion of the required follow up period; however, a patient's participation in the investigation may be discontinued. Should this occur, the reason for discontinuation must be documented in the source documents.

Patients must be informed about their right to withdraw from the investigation at any time and for any reason without sanction, penalty or loss of benefits to which the patient is otherwise entitled and withdrawal from the investigation will not jeopardize their future medical care or relationship with the investigator. Patients will be asked to specify the reason for the termination, but have the right not to answer.

The investigator may decide to withdraw a patient from the investigation at any time.

The patient's future care will not be influenced by a decision, voluntary or otherwise, to withdraw from the investigation. All reasonable efforts should be made to retain the patient in the clinical investigation until completion of the investigation.

Reasons for patient's withdrawal include, but are not limited to:

- Patient refuses to continue participating in the investigation (refuse all subsequent testing/follow up)
- Patient does not meet the inclusion/exclusion criteria prior to baseline procedure
- Patient is deceased (cause must be documented)
- Patient's non-compliance
- Patient's participation is terminated by the PI or investigator, although the patient consented, since participation is no longer medically justified
- Patient is 'lost to follow up': Patient does not adhere to the scheduled follow up visits but has not explicitly requested to be withdrawn from the clinical investigation. (This does not apply to missed visits). Site personnel should at all times make all reasonable efforts to locate and communicate with the patient in order to achieve patient compliance to the scheduled follow up visits. A patient will be considered 'lost to follow up' after
 - A minimum of 2 phone calls from a physician or delegate at the investigational site have been attempted to reach the patient. These 2 phone calls need to be documented in the patient's hospital records.
 - And a certified letter has been sent to the patient's last known address or general practitioner (GP). A copy of this letter should be maintained in the patient's hospital records. If these attempts are unsuccessful,

Note: If a patient misses one or more of the scheduled follow up visits, this will be considered as a missed visit. The patient may therefore still return for subsequent visits and will not be excluded from the investigation. The missed visits will be considered a protocol deviation.

If the patient misses two consecutive scheduled follow up visits and the above mentioned attempts to contact the patient or/and GP were unsuccessful, the patient will be considered ‘lost to follow up’ and patient’s termination form should be completed. The investigator ensures that all attempts are documented in the patient’s hospital records.

7.6 Document and data control

7.6.1. Traceability of documents and data

The investigator shall ensure accuracy, completeness, legibility and timeliness of the data reported to the sponsor on the eCRF's and in all required reports. Where copies of the original source document as well as print outs of original electronic source documents are retained, these shall be signed and dated by a member of the investigation site team with a statement that it is a true reproduction of the original source document.

7.6.2. Definition of source data

Investigators shall ensure that all source documents are accurate, complete, legible, up to date, original, attributable and capable of being audited. They shall not be obscured by correction fluid or have temporary attachments (such as removable self-stick notes). Photocopies of eCRF's are not considered acceptable source documents. Source documents are original records in which raw data are first recorded. These include, but are not limited to hospital/clinic/general practitioner records, charts, diaries, X-rays, laboratory results, printouts, pharmacy records, care records, ECG. Source documents should be kept in a secure, limited access area.

7.6.3. Recording of data

Source documents shall be created and maintained by the investigation site team throughout the clinical investigation. The data reported on the eCRF's shall be derived from, and be consistent with, these source documents. Attempts to clarify any conflicting information (discrepancy) shall be documented using the appropriate option in the Electronic Data Capture (EDC) system. The eCRF's shall be validated by the principal investigator or delegated investigator. Any change or correction to data reported on an eCRF shall be tracked.

7.6.4. Review of data (source data verification)

The clinical investigation will be monitored by reviewing the electronic eCRF's approved by the investigators. During monitoring visits, reported data are reviewed with regard to being accurate, complete, and verifiable from source data (Source Data Verification). All data reported on the eCRF's should be supported by source data.

The following activities will occur:

- eCRFs will be reviewed for completeness and accuracy by sponsor.
- The investigator, co-investigator and/or delegate will be notified regarding any missing or unclear/inconsistent data.
- The investigator (co-investigator) and/or delegate will be requested to clarify or correct the inconsistency.

7.7 Monitoring

On site-monitoring will be performed during the clinical investigation in order to guarantee adherence to all applicable regulations, the clinical investigation plan and the signed clinical investigation agreement. By monitoring, the sponsor can also verify the accuracy of data collected on the accompanying eCRF's throughout the duration of the clinical investigation.

Monitoring is necessary to ensure adequate protection of the rights and safety of human patients involved in the clinical investigation and the quality and integrity of the data obtained during the clinical investigation. The sponsor will at the same time assess the investigational site and clinical investigation team on staffing and facilities to ensure the clinical investigation can continue in a safe and effective fashion.

During the monitoring visits, data reported on the eCRF shall be reviewed as specified in the monitoring plan. (Refer to section 7.7.2).

7.7.1. Designated Monitors

Only monitors qualified by education, training and experience, which have been trained on the CIP, device and its indication for use, eCRF content, use of eCRF guidelines, Monitoring Plan, relevant requirements and informed consent process will be allowed to perform monitoring activities during this clinical investigation. The monitor's qualifications and training will be documented by the sponsor. A list of monitors is available upon request.

7.7.2. Monitoring Plan

Prior to the start of the site monitoring activities for this clinical investigation, a project specific Monitoring Plan (MP) will be created and will be available upon request.

At a minimum, the Monitoring Plan will include the following:

- Frequency of monitoring visits
- % of source data verification
- Monitoring visit requirements
- Action to be taken in case of serious site non-compliance
- Monitoring report content and timelines
- Close-out visit procedures

The monitoring plan may be updated as appropriate. All revisions will be tracked.

7.7.3. National Competent Authority (NCA)/ National Regulatory Authority (NRA) Inspections

The investigator and/or delegate should contact SJM immediately upon notification of a NCA/NRA inspection at the site. A clinical monitor will assist the investigator and/or delegate preparing for the audit.

An investigator who has authority to grant access shall permit authorized NCA/NRA employees, at reasonable times and in reasonable manner, to enter and inspect any establishment where devices are held (including any establishment where devices are used or where records or results are kept).

An investigator, or any person acting on behalf of such a person with respect to the investigation, shall permit authorized NCA/NRA employees, at reasonable times and in reasonable manner, to inspect and copy all records relating to the investigation.

An investigator shall permit authorized NCA/NRA employees to inspect and copy records that identify patients, upon notice that NCA/NRA has reason to suspect that adequate informed consent was not obtained, or that reports required to be submitted by the investigator, to the Sponsor or EC/IRB have not been submitted or are incomplete, inaccurate, false or misleading.

7.8 Investigation Termination

The Sponsor reserves the right to stop the investigation at any stage, with appropriate written notice to the investigator. Possible reasons for early termination of the investigation by the sponsor, either at local, national or international level, may include, but are not limited to:

- The device fails to perform as intended

- Occurrence of USADE which cannot be prevented in future cases
- Sponsor's decision
- Request from regulatory bodies
- Request of EC(s)

The investigation will then be terminated according to applicable regulations.

The investigator may also discontinue participation in the clinical investigation with appropriate written notice to the Sponsor.

7.8.1. Investigation Conclusion

The investigation will be concluded when:

- A close-out visit has been performed at each participating site
- The final report has been provided by sponsor

8 Risks and Benefits of the clinical investigation

8.1 Anticipated clinical benefits

The information collected in this clinical investigation will be added to the current knowledge and understanding of treatment options for patients with severe symptomatic aortic stenosis who require a TAVI procedure. It is expected that patients implanted with a Portico Valve will have the same benefits as patients implanted with other transcatheter valves.

8.2 Anticipated Adverse Events and Adverse Device Effects

Adverse events potentially associated with the use of transcatheter valves and their potential complications are documented in the Instructions for use. Instructions for use are available upon request.

8.3 Possible interactions with concomitant medical treatments

There are no known interactions of the Portico Valve with concomitant medical treatment. Patients experiencing an adverse event shall be treated by their treating physician or per the standard of care at the investigation site.

8.4 Steps that will be taken to control or mitigate the risks

Actions to control or mitigate risks at the clinical investigation site level will include the selection of qualified and experienced investigators and site personnel, investigators intensive device training, and strict adherence to the CIP. Data collected during this clinical investigation will include, but not limited to, echocardiography, ECG, and adverse event assessment. In addition, investigators shall be actively involved in the follow-up of the patients implanted with the transcatheter valves.

Risks shall be minimized by careful assessment of each patient prior to, during and after implant of the Portico Valve. After implantation, patients in this clinical investigation shall be followed at regular intervals to monitor their condition.

8.5 Risk-to-Benefit Rationale

The risks associated with the use of Portico Valve and transcatheter delivery system and valve loading system are anticipated to be comparable to those associated with the use of other currently available transcatheter valve and delivery systems. Patients participating in this clinical investigation are indicated for a TAVI procedure as part of their standard medical management and are subject to the risks associated with these devices.

9 Statistical considerations

9.1 Analysis population

All patients who have signed a PIC will be considered enrolled in the clinical investigation (refer to Section 4: Clinical investigation design). However, it is anticipated that there will be patients who are enrolled in the clinical investigation but will not be included in the analysis dataset.

These patients are described as follow:

- Patients who gave consent to participate in the clinical investigation but did not satisfy the inclusion and/or exclusion criteria before the index procedure (screen failure), or have been excluded from the study by the investigator before the index procedure.
- Patients who have enrolled in the clinical investigation and started the procedure, but did not have the Portico Valve implanted and are procedural exclusions due to their anatomy, circumstances related to the procedure, or physician judgment.
- Patient who died, were lost to follow-up or withdraw consent before the index procedure.

Patients enrolled in the clinical investigation and implanted with a PORTICO valve for whom a deviation related to inclusion and/or exclusion criteria is identified, should be followed throughout the study. The statistical analysis plan, will further describe how the data of these patients will be handled.

9.2 Sample size estimation

9.2.1 Cohort A

The sample size estimation is based on the primary endpoint of this study, all-cause mortality at 1 year post implant for patients having received a Portico Valve.

It is assumed that the expected mortality rate at 1 year post implant will be 22.1% ²⁰), and the total recruitment period will be 2 years; at least 608 patients are required to be at risk at 1 year post implant, in order to establish a two sided 95% confidence limit (18.8%, 25.4%) using non-parametric survival analysis with Peto's variance²¹. With a dropout rate of 10%, at least 866 patients need to be recruited.

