9.3 Primary endpoint analysis

The primary endpoint analysis will only include patients from Cohort A.

Non-parametric survival analysis will be used to calculate the mortality rate at 1 year post index procedure and build its 95% confidence limit. The corresponding variance will be computed using Peto's formula for survival analysis. The survival time will be calculated as the number of days between the implant date and the death date for the patients who die at 1 year (365 days) post implant. And for the patients who are considered as censored (loss to follow up, explanted, etc.), the survival times will be calculated as the number of days between the implant date and the last known adverse event or the last documented contact date before 1 year follow up. A Kaplan-Meier curve with the cumulative survival rate will also be presented.

A Cox regression model can be used for further explanatory analysis of the relationship of the prognostic factors and the mortality. These factors will include baseline factors such as age, gender, NYHA class etc., and other factors defined by steering committee can also be analyzed.

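### Section 9.2.1 allows for deaths twice: (18.8%, 25.4%) is the interval for 608 patients in total, not 608 still at risk at 1 year, so the stated precision and the target of 866 do not match

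*Combined protocol and SAP*

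**What the plan says.** Protocol section 9.2.1 (Cohort A) gives the whole sample-size argument in a few lines:

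- Event rate: "It is assumed that the expected mortality rate at 1 year post implant will be 22.1"%.
- Number needed and purpose: a minimum of 608 patients is "required to be at risk at 1 year post implant, in order to establish a two sided 95% confidence limit (18.8%, 25.4"%), a half-width of 3.3 points.
- Method: "using non-parametric survival analysis with Peto's variance".
- Recruitment: "With a dropout rate of 10%, at least 866 patients need to be recruited".

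Section 9.3 uses the same variance for the primary analysis: "The corresponding variance will be computed using Peto's formula for survival analysis". Neither section writes the formula out, and 9.2.1 does not show how 608 becomes 866. The minimum of 866 for Cohort A is repeated in the synopsis and in sections 5.4 and 9.2.2.

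**The concern.** The figure 608 does two jobs. As the basis of the confidence interval, it behaves like a total sample that includes the patients who die. As the basis of the recruitment target, it is a count of patients alive and under observation at 1 year. With 22.1% mortality those are different groups, and one number cannot serve for both.

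This is a single-arm study with no concurrent control, and section 9.2.1 sets no hypothesis or performance goal. The target interval is the only criterion offered for its size. If the number at risk, the interval and the recruitment target do not belong together, a reader cannot tell what precision was planned or how many patients must still be under observation to reach it.

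As an illustration, 550 patients at risk at 1 year would miss the stated minimum of 608. Yet under Peto's variance the half-width would be 1.96 × 0.779 × √(0.221/550) = 3.06 points, already inside the stated 3.3.

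**Working it through.** **Inputs, all from section 9.2.1.** Mortality p = 0.221, so survival S = 0.779; two-sided 95%, z = 1.96; half-width w = 0.033; dropout 10%; 608 at risk; 866 recruited. The "the total recruitment period will be 2 years" input is not needed for any figure below.

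**1. Reproducing 608 and the interval.** The binomial size for a total sample without censoring is

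N = z² p(1 − p)/w² = 1.96² × 0.221 × 0.779/0.033² = 607.3, rounded up to 608.

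Conversely, 1.96 × √(0.779 × 0.221/608) = 3.30 points, which is (18.8%, 25.4%), exactly as stated.

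**2. Reproducing 866.**

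| Route from 608 | Result |
|---|---|
| Dropout only: 608/0.9 | 676 |
| Dropout as 608 × 1.1 | 669 |
| 608/(1 − 0.221 − 0.1) | 895 |
| 608/0.779 × 1.1 | 859 |
| 608/0.779/0.9 | 867.2 |
| 608/0.78/0.9 | 866.1 |

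Only division by survival as well as by 0.9 gives 866. The gap between 867.2 and 866 is rounding of the survival rate and carries no weight.

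**3. Precision with 608 at risk.** Peto's variance is S²(1 − S)/n(t), where n(t) is the number still at risk. With n(t) = 608:

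1.96 × 0.779 × √(0.221/608) = 2.91 points, an interval of (19.2%, 25.0%).

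**4. A check that does not depend on the name of the formula.** With no dropout, 608 at risk at 1 year means 608/0.779 = 780 implanted. The ordinary binomial half-width for 780 patients is 1.96 × √(0.779 × 0.221/780) = 2.91 points, the same as in step 3.

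**5. What the stated interval needs.** Solving Peto's formula for w = 0.033:

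n(t) = 1.96² × 0.779² × 0.221/0.033² = 473.1, so 474 at risk.

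That corresponds to about 608 implanted with no dropout (473.1/0.779 = 607.3), or about 676 with 10% dropout. The excess is 866 − 676 = 190, and 190/676 = 28%.

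**6. What 866 recruits deliver.** Expected at risk: 866 × 0.779 × 0.9 = 607.2. Trials of 866 patients were simulated with exponential time to death (22.1% at 1 year) and 10% dropout, 4,000 for each dropout pattern. Half-widths of the 1-year Kaplan-Meier estimate, in points:

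| Dropout pattern | At risk at 1 year | Peto | Greenwood | Empirical (1.96 × SD) |
|---|---|---|---|---|
| Spread through the year | 607 | 2.91 | 2.84 | 2.85 |
| All immediately after implant | 607 | 2.91 | 2.91 | 3.00 |

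All are below 3.30. Simulation of 676 patients gave 3.30 (Peto), 3.21 (Greenwood) and 3.26 (empirical), which is the stated precision.

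**The case against.** The strongest reply is that the protocol prints no formula. If the authors meant S(1 − S)/n(t), with n(t) the number at risk, then 608 at risk does return (18.8%, 25.4%), 608/0.78/0.9 does give 866, and every printed figure agrees. On that reading 608 was never a total sample, and the primary analysis would report a half-width of about 3.3 points, as planned.

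Part of this stands: the documents cannot show which expression was used, so how the error arose is an inference. The stated precision is still wrong. S(1 − S)/n(t) does not reduce to the binomial variance when nobody is censored; it is too large by 1/0.779 = 1.28. Step 4 and the simulation put the real half-width at about 2.8 to 3.0 points on either reading. If that form was intended, section 9.3 carries it into the primary analysis, where the interval would be too wide.

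Three further points are fair:

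- The error is conservative: 866 recruits give the stated precision or better.
- No rule in the protocol makes 608 at risk a test of adequate follow-up, so the 550 example is only illustrative.
- Enrolment is counted from consent (section 5.9), and patients not implanted leave the analysis (sections 5.10.3 and 9.1). Section 9.2.1 does not say whether the 10% covers them. If it does not, 866 recruits will leave fewer than 607 at risk.

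**Conclusion.** The concern holds. The interval belongs to 608 patients in total, while the recruitment target treats 608 as patients still at risk, so deaths are counted in both steps. The stated half-width is 3.3 points; 866 recruits deliver about 2.9 by Peto's variance. The stated 3.3 points need about 474 at risk, or about 676 recruits.

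These figures assume 22.1% mortality at 1 year and a 10% dropout that covers all losses. The 2.91 and the 474 use S²(1 − S)/n(t), but the conclusion that 608 at risk gives better than 3.3 points does not depend on that form. No validity is lost, so this should be corrected but does not threaten the study.

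**What to change.** Restate section 9.2.1 and leave enrolment as it is:

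1. Write out the variance as S²(1 − S)/n(t), with n(t) the number at risk at 1 year, and refer to the same expression in section 9.3.
2. State that 866 recruits, with 22.1% mortality and 10% dropout, give about 607 at risk at 1 year and an expected 95% interval of (19.2%, 25.0%). Say whether the 10% includes patients who consent but are not implanted.
3. State separately that about 474 at risk is the minimum for (18.8%, 25.4%) under the same assumptions, so that it is not read as a new enrolment target.

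The cost is a few sentences. Recruitment, follow-up and the analysis method do not change, provided the analysis uses the formula as written out.

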9.2.2 Cohort B

The anticipated number of patients who participated to a SJM-sponsored Regulatory or First-In-Human trial conducted in Europe and who will participate to the clinical investigation will be approximately 180.

The total population to be enrolled in the clinical investigation is at least 866 for COHORT A, added up with any additional patients enrolled in Cohort B, to a maximum of 1046 patients in total.

